NDA	- NATIONAL DRUG AUTHORITY
SOMREC	- SCHOOL OF MEDICINE RESEARCH AND ETHICS COMMITTEE
TXA	- TRANEXEMIC ACID
UBTS	- UGANDA BLOOD TRANSFUSION SERVICES

ABSTRACT

Background: Major Perioperative blood loss is one of the complications of open femoral shaft fracture intramedullary nailing surgery with average blood loss estimated at 1500mls. There is need for strategies to reduce on this blood loss. Antifibrinolytics such as tranexemic acid have been successfully used to reduce perioperative blood loss in other orthopaedic procedures.

However effectiveness of tranexemic acid use during open femoral shaft fracture intramedullary nailing surgery has not been studied in our setting.

Aim: To assess the effectiveness of intravenous tranexemic acid in reduction of perioperative blood loss, transfusion rates in patients undergoing open femoral shaft fracture intramedullary nailing surgery.

Methods: This will be an open label single arm study. Patients scheduled for open femoral shaft fracture intramedullary nail fixation surgery will receive preoperative tranexemic acid at 15mg/kg. Blood loss using difference between pre and post-operative hemoglobin, blood transfusion rates and adverse events in the peri operative period will be measured.

Utility: The results of this study will reveal effectiveness of tranexemic acid in reducing perioperative blood loss during open femoral shaft fracture surgery in this setting. This information will be useful in designing protocols for prevention of perioperative blood loss for femoral shaft fracture surgery.

OPERATIONAL DEFINITIONS

Peri-operative

- Period from start of surgery to 72 hours after the Surgery

ORIF

- Open intramedullary nailing of femoral shaft fractures.

CHAPTER ONE

INTRODUCTION

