Tranexemic Acid (Kapron, Egypt) 500mg / 5ml ampoule will be used. Drug will be prepared at 15mg/kg by the anaesthetist who will administer it for over 10mins to prevent drug induced hypotension, dizziness vomiting and nausea. 10mins before skin incision so as to achieve optimal plasma and interstitial concentrations.

All patients will receive pre-operative antibiotics, before the surgery.

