3.7.4 Surgical Time

Time of skin incision and last skin suture will be documented to determine surgical time. It will be presented in minutes.

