3.8.2 Outcome Variables

- . Primary Outcome: Perioperative blood loss –Will be represented as difference in the 2 hour pre-operative and 72 hour post-operative hemoglobin concentration in g/dl.
- . Secondary Outcome: Blood Transfusion – will be represented as the number of blood units. 450mls of whole blood will equate to 1 unit of whole blood. 200mls of packed cells will equate to 1 unit of whole blood.
- . Secondary Outcome: Safety – Will be described as adverse events secondary to administration of Tranexemic Acid observed in patients in the study during the perioperative period.
 - Anaphylaxis
 - Dizziness
 - Hypotension
 - Nausea and Vomiting
 - Diarrhoea
 - Thrombo -embolic Events
 - Others.....

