APPENDIX II: Data Collection Sheet

Study Number.....

Date of Surgery

Study Arm A
 B

A. Patient information

1) Inpatient number 2) Age (yrs)

3) Sex: M F 4) Weight (kg)

B. Pre-operative Data

1) Duration of Injury (Days) 2) Fracture Pattern (AO / OTA)

 A B C

3) Preoperative Hemoglobin (g/dl) 4) Platelet Count

5) aPTT 6) PT-INR

C. Procedure Data

1) Type of Anaesthesia 2) Time : Start of Surgery

GA Regional

3) Time : End of Surgery 4) Duration of Surgery (hrs)

5) Nailing Approach 6) Whole Blood Units Transfused

Ante grade / Retrograde

7) Adverse Event/s Y N (Describe Event/s)

D. Postoperative Data

1) Whole Blood Units Transfused 2) 72hr Post-operative Hemoglobin (g/dl)

3) aPTT

4) PT-INR

Peri-operative Blood Loss (g/dl)

$$= \text{Pre-opHb} - (\text{Post-opHb} + \text{Blood Units})$$

$$= \dots - (\dots + \dots)$$

$$= \dots \text{ (g/dl)}$$

Intraoperative and Post-operative Adverse Events and complications

Pre / Intraoperative Period				Comments
DVT / TEE	Nausea Vomiting Diarhoea	Anaphylaxis Dermatitis	Hypotension	
Others				
Day 1				Comments
DVT / TEE	Nausea Vomiting Diarhoea	Anaphylaxis Dermatitis	Hypotension	
Others				
Day 2				Comments
DVT / TEE	Nausea Vomiting Diarhoea	Anaphylaxis Dermatitis	Hypotension	

Others				
Day 3				Comments
DVT / TEE	Nausea Vomiting Diarhoea	Anaphylaxis Dermatitis	Hypotension Dizziness	
Others				
Day 3-14				Comments
DVT / TEE	Nausea Vomiting Diarhoea	Anaphylaxis Dermatitis	Hypotension Dizziness	
Others				

**APPENDIX III: Transfusion Guidelines for patient's participating in
“EFFECTIVENESS OF PREOPERATIVE INTRAVENOUS TRANEXEMIC
ACID ON REDUCTION OF PERIOPERATIVE BLOOD LOSS IN OPEN
INTRAMEDULLARY NAIL FIXATION OF FEMORAL SHAFT FRACTURES
IN MULAGO” Study**

Category 1	Circle	Transfusion Criteria
Intraoperative Hemoglobin Concentration of < 7g/dl	YES / NO	Transfuse with 1 Unit of WB or PRBC if 1 Criteria in category 1 is met
Category 2		
Intraoperative Hemoglobin Concentration of < 10g/dl	YES / NO	Transfuse with 1 Unit of WB or PRBC if 1 criteria in Category 2 is met together with 3 criteria in Category 3
Category 3		
Severe bleeding at the surgical site and soiling of surgical drapes and mops	YES / NO	Transfuse with 1 Unit of WB or PRBC if ≥ 4 criteria in Category 3 are met
Tachycardia	YES / NO	
Oxygen Saturation < 90%	YES / NO	
Hypotension	YES / NO	
Severe pallor of the Mucous Membranes	YES / NO	
Decreasing Levels of Consciousness	YES / NO	
Dyspnoea	YES / NO	
Angina	YES / NO	

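### The safety outcome's window, read literally, opens after the tranexamic acid infusion has begun and closes at 72 hours, so it conflicts with the adverse-event form and the 2-week follow-up, and no safety set is defined

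*Combined protocol and SAP*

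**What the plan says.** The Operational Definitions give the perioperative period as "Period from start of surgery to 72 hours after the Surgery". Section 3.8.2 defines safety as "adverse events secondary to administration of Tranexemic Acid observed in patients in the study during the perioperative period", and lists anaphylaxis, dizziness, hypotension, nausea and vomiting, diarrhoea, thromboembolic events and others. The Abstract uses the same window: "blood transfusion rates and adverse events in the peri operative period will be measured".

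Section 3.7.3 describes the dosing. The anaesthetist prepares the drug, and is the person "who will administer it for over 10mins to prevent drug induced hypotension, dizziness vomiting and nausea"; the timing is "10mins before skin incision so as to achieve optimal plasma and interstitial concentrations". Section 3.7.4 says: "Time of skin incision and last skin suture will be documented to determine surgical time".

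The collection of safety data is wider than the outcome. Section 3.7.7 follows patients for 2 weeks after surgery. The adverse-event table in Appendix II is headed "Intraoperative and Post-operative Adverse Events and complications", but its first row covers the pre-operative as well as the intraoperative period, and its last row covers Days 3 to 14. Section 3.12, Objective 3, plans descriptive proportions of adverse events in the study group. It names no time window and no safety analysis set.

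**The concern.** Safety is part of the general objective (1.6.1) and is the second of the two secondary objectives (1.6.2.2). There is no control arm, so the observed proportions are the whole safety result. Their numerator and denominator need to be unambiguous.

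At the opening end, exposure to the drug begins before the defined window does. Section 3.7.3 itself links hypotension, dizziness, vomiting and nausea to the administration, so the minutes left out are ones in which the protocol expects drug effects to be possible. At the closing end, the window stops at 72 hours although patients are watched for thromboembolic events for 2 weeks.

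Both kinds of event would be on the form, yet neither would meet the outcome definition. Whether they enter the reported rates is then left to whoever does the analysis, possibly after the events are known. The same holds for a patient who receives the drug and whose operation does not go ahead.

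**Working it through.** **Opening of the window.** Put skin incision at 0 minutes.

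- The infusion takes 10 minutes (3.7.3). If the stated 10 minutes before incision marks the start of the infusion, it runs from −10 to 0. If it marks the end, the infusion runs from about −20 to −10. The text allows either reading.
- The perioperative period opens at the start of surgery. That phrase is not defined, but 3.7.4 counts surgical time from skin incision. Section C of Appendix II has a field for the start of surgery and none for incision, so the incision time would be entered there. Taking the start of surgery as 0 is therefore a strong inference.
- On either reading, the 10 to 20 minutes from the start of infusion to incision come before the window.
- Section 3.8.2 counts events observed during the period. A reaction that begins after incision, or is still present then, counts. Only a reaction confined to the time before incision does not.

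**Closing of the window.** Follow-up is 14 × 24 = 336 hours after surgery. The window covers the first 72, which leaves 336 − 72 = 264 hours, or 11 of the 14 days, outside it. Most of the last row of the form lies in that stretch.

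**Definition, form and analysis side by side.**

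| Period | Outcome definition (3.8.2 with Operational Definitions) | Form (Appendix II) | Analysis (3.12) |
|---|---|---|---|
| Start of infusion to incision | Outside | Recorded | No window stated |
| Incision to 72 hours | Inside | Recorded | No window stated |
| 72 hours to Day 14 | Outside | Recorded | No window stated |
| Dosed, operation abandoned before incision | No start of surgery, so no defined period | Can be recorded in the first row | Study group not defined for this case |

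**Scale.** The planned N in 3.6.1 is reproduced: 2 × 1.56² × (1.96 + 0.84)² / 0.993² = 38.7, taken as 39; 39/0.9 = 43.3, taken as 43. Here N serves only as a denominator.

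- One event is 1/43 = 2.3 percentage points.
- With exact binomial limits, leaving out a single event changes 1/43 (95% CI 0.06% to 12.3%) to 0/43 (0% to 8.2%).
- The documents give no rate for pre-incision reactions. Under assumed rates p of 1%, 2%, 5% and 10%, the chance of at least one in 43 patients, 1 − (1 − p)^43, is 35%, 58%, 89% and 99%. These rates are illustrations, not estimates.

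**The case against.** The best answer is that nothing is lost in practice. The first row of the form covers the pre-operative period and has entries for anaphylaxis or dermatitis, hypotension, and nausea, vomiting and diarrhoea, with space for other events and comments. Section C asks separately for any adverse event. Section 3.7.7 requires serious events to be reported within 24 hours of occurrence, with no perioperative limit. Section 3.12 counts events in the study group without restricting the time. The protocol also uses the word perioperative loosely: perioperative blood loss takes its baseline haemoglobin 2 hours before surgery, outside the literal definition. On this view the authors never meant the definition to cut off safety events.

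Much of this stands, and it rules out several stronger readings that a reader might infer:

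- *That infusion reactions in general are missed.* Only those confined to the time before incision fall outside; any still observed after incision count.
- *That a patient whose operation is abandoned leaves the denominator.* No rule removes such a patient. The documents are silent, which is a different fault.
- *That reported rates will be too low.* This would require the team to record events and then discard them under the definition. The text permits that but does not prescribe it, and no reaction rate is given from which to size it.
- *That dizziness cannot be recorded early on.* It is absent from the Pre/Intraoperative, Day 1 and Day 2 rows as extracted, but the table is visibly broken, and each row allows other events.

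What the objection does not remove is the stated rule. Section 3.8.2 defines the outcome by a period that excludes events the form is built to collect, and 3.12 does not say which governs. The baseline haemoglobin is a reference measurement and does not show that the adverse-event window opens earlier.

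**Conclusion.** The point holds as an internal conflict of moderate severity. Taken literally, the safety outcome leaves out events confined to the time between the start of infusion and incision, and events after 72 hours, including thromboembolic ones. The form and the follow-up cover both periods. The analysis section settles neither the window nor whether a patient who is dosed but not operated on is counted.

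The opening-end conclusion assumes that the start of surgery means skin incision, which 3.7.4 and the form support but do not state. The closing-end conclusion needs no such assumption. The effect on the results cannot be estimated from the documents; each omitted event would be worth 2.3 percentage points at N = 43. The finding concerns what is reported, not what is collected.

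**What to change.** - **Section 3.8.2:** give safety its own window, from the start of the tranexamic acid infusion to the end of the 2-week follow-up.
- **Section 3.12, Objective 3:** state the denominator as every patient who received any study tranexamic acid, whether or not surgery proceeds, and refer to the window in 3.8.2.
- **Operational Definitions and Abstract:** say that the perioperative definition does not set the safety window. Leave the blood-loss and transfusion windows unchanged.
- **Appendix II:** make the heading of the adverse-event table agree with its rows, and check in the source form that Dizziness is printed in every row.

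The cost is a few sentences and a small form edit, with no added visits or tests. The downside is that reported adverse event rates may be slightly higher. The change should be made before any safety data are reviewed, so that neither the window nor the denominator is chosen with the events in view.

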1.1 Background

Major orthopaedic procedures are often associated with major blood loss.(1, 2) Open Reduction and Internal Fixation (ORIF) of femoral shaft fractures is one of major orthopaedic procedures associated with major perioperative blood loss estimated at 1500mls in a developing world operating theatre.(3)

Worldwide major blood losses cause hemodynamic instability and severe anaemia, hence a need for allogeneic blood transfusions that are associated with a number of complications such as (e.g., mismatched transfusion, allergic reactions, transmission of infections, and acute lung injury).(4-6) Furthermore, allogeneic transfusions are also associated with increasing costs such as prolonged hospital stay and the cost of processing, handling, administration of blood products.

Amount of perioperative blood loss during major orthopaedic procedures can be multifactorial with patient and institutional factors. Patient factors do include but not limited, inability to cauterize or coagulate bony surfaces resulting in uncontrollable hemorrhage and increased fibrinolysis as a result of surgical stress. (2, 7) On the other hand institutional factors include availability of electro cautery and fluoroscopy guided intramedullary fracture fixation are believed to reduce intraoperative blood loss.(3)

In the developed and under developed world the need to minimize perioperative blood loss during orthopaedic procedures has been a focus of multiple strategies addressing both patient and institutional factors. (e.g. Hypotensive epidural anesthesia (HEA), Platelet rich plasmapheresis, Acute normovolemic hemodilution (ANH), Cell salvage (scavenging), Anti-fibrinolytics, Fibrin sealants) (1, 8, 9)

Tranexemic acid (TXA) has been used to achieve hemostasis in a number of orthopaedic and non orthopaedic procedures. This is because TXA is an antifibrinolytic agent, a synthetic lysine product that competitively inhibits plasminogen activation to plasmin, and at much higher concentrations, a noncompetitive inhibitor of plasmin, i.e., actions similar to aminocaproic acid. This action prevents dissolution of the fibrin clots stabilizing the clots at the surgical site hence

achieving and maintaining hemostasis.(10-12). TXA has a wide therapeutic window and despite theoretical risk of thromboembolic events has been found to be safe for use in major orthopaedic procedures.(1, 12, 13)

Despite studies in developed countries showing intravenous administration of TXA leads to significant reduction in perioperative blood loss and blood transfusion requirements in orthopaedic surgeries (Spine, Hip Arthroplasty, Knee Arthroplasty)(12, 14, 15) TXA use can be further extended to address need for reduction of perioperative blood loss in ORIF.

A study to determine efficacy of preoperative intravenous TXA on perioperative blood loss in patients undergoing Open intramedullary nail fixation of femoral shaft fractures in Mulago National Referral Hospital.

1.2 Problem Statement

Closed reduction intramedullary nail fixation under guidance of fluoroscopy is the most used treatment for femoral shaft fractures. However in resource limited settings with lack of standard theatre facilities, open intramedullary nailing is done with aid of jig and target arm and this increases the risk of substantial peri-operative blood loss.(16) Kajja et al(3) in 2009 showed that ORIF in the resource limited settings leads to a substantial peri-operative blood loss of >1500ml.

This substantial peri-operative blood loss puts a stress on the limited hospital blood bank, financial and human resources, and limits access of the sparse blood units for others in need of blood transfusion. The costs to have a unit of safe blood delivered to the hospital have been estimated to be \$45 in Uganda and \$150 - \$400 elsewhere (17-20).

TXA has been used to achieve hemostasis in number of orthopaedic and non orthopaedic procedures with significant reduction in peri operative blood loss and blood transfusions (12, 15, 21). In addition, TXA has a wide therapeutic window, is affordable and readily available compared to other strategies to minimize perioperative blood loss such as fibrin sealants. However TXA has not been applied in femoral shaft surgeries to reduce blood loss in our settings.

1.3 Study Justification

There is need for an affordable, readily available and safe method of reducing perioperative blood loss in ORIF such as TXA.

Use of TXA for this indication has not been assessed and its effect is unknown in our setting.

This study will establish the role of TXA in ORIF in a resource limited theatres. Further providing clinicians a cheap and readily available option to use in reduction of blood loss during open femur shaft fracture Intra Medullary Nailing.

Institutions like hospitals and Ministry of health can use these findings to draw up protocols and guidelines for prevention of perioperative major blood loss in patients undergoing ORIF.

The study will set a baseline on which further studies on the use of Tranexemic Acid in other orthopaedic and non orthopaedic surgical procedures may be based.

1.4 Research Hypothesis

Intravenous Tranexemic acid given preoperatively at 15mg/kg before open femoral shaft fracture intramedullary nailing will reduce average perioperative blood loss of 3.31 g/dl and perioperative transfusion rates by 30%.

1.5 Research Question

What is the effectiveness of pre-operative intravenous Tranexemic acid in reduction of perioperative blood loss in open intramedullary nail fixation of femoral shaft fractures in Mulago Hospital?

1.6 Objectives

1.6.1 General Objective

To determine the effectiveness and safety of pre-operative intravenous Tranexemic Acid 15mg/kg on reduction of perioperative blood loss in adult patients undergoing open intramedullary nail fixation of femoral shaft fractures in Mulago National Referral Hospital.

1.6.2 Specific Objectives

1.6.2.1 Primary Objective

1. To determine the effectiveness of pre-operative intravenous Tranexemic acid 15mg/kg reduction of perioperative blood loss as estimated by difference in 72 hour postoperative and 2 hour preoperative Hemoglobin concentration in patients undergoing open intramedullary nail fixation of femoral shaft fractures in Mulago National Referral Hospital.

1.6.2.2 Secondary Objectives

1. To determine effectiveness of pre-operative intravenous Tranexemic acid 15mg/kg on reduction of transfusion rates in patients undergoing open intramedullary nail fixation of femoral shaft fractures in Mulago National Referral Hospital.
2. To determine the safety of pre-operative intravenous Tranexemic acid 15mg/kg in patients undergoing open intramedullary nail fixation of femoral shaft fractures in Mulago National Referral Hospital.

1.7 Conceptual Framework

Demographics

- Age
- Sex
- Weight

Surgery

- General Anaesthesia
- Regional Anaesthesia
- Antegrade Nailing Technique
- Retrograde Nailing

Clinical

- Pre-operative Hemoglobin
- Duration of Injury
- Fracture Pattern (AO / OTA)

**Intravenous
Tranexemic Acid**
15mg/kg, 10min
before Skin Incision

- Reduction in Blood transfusion

- Reduction in Perioperative blood loss

Adverse Events

- Anaphylaxis
- Dizziness
- Hypotension
- Nausea and Vomiting
- Diarrhoea
- Thrombo -embolic Events
- Others

CHAPTER TWO

LITERATURE REVIEW

2.1 Introduction

The orthopaedic surgeon is faced with numerous perioperative complications arising from modern day orthopaedic surgery. Excessive intraoperative and postoperative blood loss, is a common occurrence attributed orthopaedic surgeries, being more invasive procedures as compared to other surgical specialties. Amongst the many strategies attempted to reduce perioperative blood loss in modern day orthopaedic procedures is use of antifibrinolytic agents such as Tranexemic Acid. (8)

2.2 Tranexemic Acid

Okamoto et al discovered trans-4-Aminomethyl-Cyclohexanecarboxylic Acid (Tranexamic acid) as a potent antifibrinolytic superior to the previously used antifibrinolytic lysine analogue Epsilon-Aminocaproic Acid (EMCA).(22) TXA is an Antifibrinolytic Agent. TXA is a synthetic derivative of the amino acid lysine with antifibrinolytic activity. With strong affinity for the five lysine-binding sites of plasminogen, TXA competitively inhibits the activation of plasminogen to plasmin, resulting in inhibition of fibrinolysis ensuring stabilization of clot: at higher concentrations, this agent noncompetitively inhibits plasmin. This agent has a longer half-life, is approximately ten times more potent, and is less toxic than aminocaproic acid, which possesses similar mechanisms of action.(10)

Tranexemic acid has two formulations i.e. Oral tablet and injectable solution, however in surgery Injectable solutions have been mostly used due to the rapid distribution in intracellular and extracellular compartments. Despite several clinical studies proving the efficacy of TXA with single or multiple boluses of different sizes with or without subsequent infusions, no consensus has been reached regarding the optimal regimen for intravenous TXA administration. Previous studies have established the need for a therapeutic plasma concentration of 10 ng/ mL and an 80% reduction in the activity of plasminogen activator for adequate suppression of fibrinolysis in

tissues, the dosage of 10-15mg/kg has been found to achieve this concentration within 10 mins of administration in the knee Arthroplasty surgeries. (23) (24) (25)

TXA has been reported to be a safe drug with a large therapeutic window and adverse effects mostly documented at high doses >20mg/kg. Some of the common adverse effects of intravenous TXA reported are.

- Hypotension, this is associated with rapid infusion, infusion rate of at most 1 mL per minute is recommended.
- Gastrointestinal disturbances (nausea, vomiting, diarrhea)
- Allergic dermatitis, giddiness
- The risk of thromboembolism among patients receiving TXA has been shown not to be different from those not receiving TXA (10, 23, 26)

